4.4 MANAGEMENT OF POTENTIAL STUDY RISKS

Risks

There is no additional risk onto the already well-established risks of catheter ablation of PVC/VT/VF.

CT scan (only if patient has a contra-indication for CMR scans)

The scan is acquired in a single breath hold during expiration from the level of the acromial processes to the dome of the diaphragm and starts with the 80 mls injection of contrast agent with Omnipaque 350 mg/ml followed by 20 mls of saline at a flow rate of 5 mls per second.

Cardiac CT performed on retrospective ECG gated CT imaging (end diastole) using tube modulation technique and adjusting the kvp according to BMI (100 kvp if BMI<30 and 120 kvp if BMI >30 kg/m²). There could be adverse reactions to the intravenous contrast agent. Patients with renal impairment would be excluded from this study.

Clinical protocols are in place to manage anaphylaxis which is however very rare.

Mapping with VIVO system and catheter ablation

We anticipate that mapping with VivoTM system will not prolong the overall procedure duration or any technical aspect of the catheter ablation. As it is a non-invasive system intended to provide an accurate localization of the arrhythmia foci, most part of the work will be carried out in a pre-procedural phase (anatomy reconstruction from the pre-acquired scan, ECG template acquisition and arrhythmia foci localization on the virtual model). Also, the radiation exposure time for operator and patient is overall comparable to conventional procedures.

We will use an amended version of the already routinely used consent form for PVC/VT ablation used in the Trust to outline the inherent risk of an ablation for PVCs/VT/VF.

5. STUDY OBJECTIVES

5.1 PRIMARY OBJECTIVE

Our hypothesis is that patients with PVCs/VT who must undergo catheter ablation can benefit from a VIVO non-contact mapping and guided ablation in terms of efficacy to decrease the procedural time of the ablation and acute success.

5.2 SECONDARY OBJECTIVES

We will assess the efficacy of Vivo non-invasive mapping system guided ablation with regards to safety and clinical outcome. Furthermore, we will assess if the precise 3D a priori knowledge of the arrhythmia exit site shortens the procedure and how large thereby the reduction of costs per single case is, as compared to historic controls.

6. STUDY DESIGN

6.1 OVERALL DESIGN

This is a prospective, single arm, observational and feasibility study, which will recruit 15 non-selected patients, with structurally normal heart, with a conventional indication for catheter ablation of PVCs/VT. The follow up will be of three months. The study will also include another retrospective cohort, including age & gender matched patients, without cardiac structural disease, with a conventional indication for catheter ablation of PVCs/VT from the last 5 years' database of the same operator. For this second retrospective cohort there will be no follow-up.

6.2 TREATMENT AND RATIONALE

[figure not shown]
A three month follow up period after ablation of PVC/VT is a long enough time frame which allows us to assess the effect of the ablation on suppression/reduction of arrhythmia burden. Patients will be followed-up at 3 months following the ablation procedure. Early recurrences will be treated by uptitrating/changing/addition of anti-arrhythmic medication and/or DCCV if persistent arrhythmia. If further arrhythmia occurs despite these measures, a re-ablation procedure will be offered. If further episodes occur, patients can be offered a second ablation procedure or continuation of medical management.

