6.3 SCHEMATIC OF STUDY DESIGN

	Pre-ablation	Pre-discharge	3 months
12 lead ECG		X (routine)	X (routine)
Telemetry	X (routine)		
Contrast CT scan or non-contrast CMR for roadmap	X (routine)		
TTE		x (routine)	
Symptom questionnaire	X (research)		X (research)
Clinic Visit			X (EP OPC)
ECG Holter (Mortara)	X (research)		X (research)

**VIVO™ non-invasive Time Assessment
Protocol**

(Vivo protocol)

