10.2 BASELINE ASSESSMENTS

- Detailed past medical history including first diagnosis of PVC/VT and related symptoms
- Physical examination
- ECG
- Evaluation of PVC/VT related symptoms
- Standard laboratory tests
 - complete blood count
 - coagulation studies
 - serum creatinine and electrolytes
 - liver function tests
 - CRP

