10.4 SUBSEQUENT ASSESSMENTS

Follow-up

3 months (follow-up visit – study completion - endpoints assessment)

The next scheduled follow-up visit after discharge will be at approximately three months post PVC/VT ablation. The following assessments will take place:

- Patient's symptoms (questionnaire) and clinical assessment
- Review of medication
- 12-lead ECG
- 12-lead Holter (Mortara)
- If high PVC/ VT burden at 3 months, either therapy change or repeat ablation (according to patient and physician preference).

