10.5 SUMMARY CHART OF STUDY ASSESSMENTS

	Pre-ablation	Pre-discharge	3 months
12 lead ECG		X (routine)	X (routine)
Telemetry	X (routine)		
Contrast CT scan or non-contrast CMR for roadmap	X (routine)		
TTE		x (routine)	
Symptom questionnaire	X (research)		X (research)
Clinic Visit			X (EP OPC)
ECG Holter (Mortara)	X (research)		X (research)

Follow up

3 months
Follow-up visit

RHYTHM & SAFETY
Review therapy, allow Re-ablation if necessary using same methodology
Assess recurrences by 12-lead Mortara Holter

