14.2.2 Secondary endpoints

- To assess clinical outcome (suppression of reduction of PVCs burden/VT at 3 months F/U)
- To assess safety
- To assess economical outcome (cost reduction per case)

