14.3 STATISTICAL ANALYSIS PLAN

Descriptive statistic data with regard to baseline and procedural variables will be reported; continuous variables will be expressed by mean \pm standard deviation or median and interquartile range (25th, 75th percentile), depending on the normality of distribution; categorical variables will be summarized by frequencies and percentages. The outcome of radiofrequency ablation on the entire cohort of patients will be presented in the form of percentage of patients free from symptomatic or documented arrhythmia or with only mild symptoms related to arrhythmia recurrence.

Depending on the severity of symptoms and documentation of tachycardia during follow-up, patients will be divided into two groups (success/recurrence). Baseline characteristics and procedural variables will be compared between these two groups by student t-tests, Mann Whitney U tests, or Fisher's exact test where appropriate in order to identify those variables associated with better mid/long term outcomes. A two-tailed p value <0.05 will be considered statistically significant. Intra-patient improvement from baseline to 6 months follow-up visit will be assessed by McNemar's test. Freedom from PVC/VT will be assessed as a time-dependent variable using Cox proportional hazard models.

To judge if ablation strategy using Vivo mapping system is as successful in achieving the clinical endpoint, we will compare the procedure parameters as well as the outcome of this trial to age & gender matched procedures of the same operator from the last 5 years' database.

To measure the strength of association between the acute successes (PVC/VT suppression at the end of the ablation) and outcome, a McNemar test will be performed. Data will be analyzed using SPSS version 18 (IBM Corporation).

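### The 3-month arrhythmia result is read as the effect of the ablation, but anti-arrhythmic drugs may change in between, drug state is not a named baseline item, and the success rule ignores it

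*Combined protocol and SAP*

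**What the plan says.** - **Purpose of follow-up (6.2).** Three months is said to be long enough because it "allows us to assess the effect of the ablation on suppression/reduction of arrhythmia burden".
- **Endpoint (14.2.2).** The clinical secondary endpoint is "To assess clinical outcome (suppression of reduction of PVCs burden/VT at 3 months F/U"), which I read as suppression or reduction.
- **Recordings (6.3, 10.5).** "ECG Holter (Mortara") is scheduled as a research test before ablation and again at 3 months. The follow-up box in 10.5 adds "Assess recurrences by 12-lead Mortara Holter".
- **Treatment between the recordings (6.2).** Early recurrences are to be managed by "uptitrating/changing/addition of anti-arrhythmic medication", with cardioversion if arrhythmia persists and re-ablation on offer after that.
- **Drug information.** "Review of medication" is listed in 10.4, at 3 months. The baseline list in 10.2 has history, examination, ECG, "Evaluation of PVC/VT related symptoms" and laboratory tests. Neither it nor the screening list in 10.1 names medication.
- **Analysis (14.3).** Success is defined by symptoms and documented arrhythmia, with mildly symptomatic recurrence allowed. In addition, "Intra-patient improvement from baseline to 6 months follow-up visit will be assessed by McNemar's test". No drug term appears, and 14.6 adds no further considerations.

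**The concern.** A within-patient change can be credited to the ablation only if other influences on the arrhythmia are held constant or are recorded well enough to be separated. Here a second treatment aimed at the same arrhythmia may be started or increased between the two recordings, and recurrence after ablation is what triggers it. A patient in whom the ablation failed and a drug then worked can look the same at 3 months as one in whom the ablation worked.

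The bias can also run the other way: if a drug is reduced or stopped after a good result, a true reduction is partly hidden. No parallel comparison helps, because 6.1 plans no follow-up for the historical cohort.

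At stake is the interpretation of the clinical secondary outcome. Section 14.1 says the pilot is meant to lead to a powered multicentre trial, so a success rate that mixes drug and ablation effects could be carried into its planning.

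**Working it through.** The plan states no figure on this point. The 15 patients were chosen without a power calculation (14.1), so there is nothing to reproduce. The check is a reading of the text, followed by illustrations with assumed inputs.

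**1. Where drug state is specified**

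- Eligibility (synopsis, 7.1, 7.2): no anti-arrhythmic drug criterion, washout or stable-dose condition.
- Screening and baseline (10.1, 10.2): medication not named.
- Pre-ablation recording (10.3): drug state not stated. If no arrhythmia is seen, it may be provoked by exercise, isoprenaline or atropine.
- Schedule tables (6.3, 10.5, appendix): no medication row.
- 3 months (10.4): medication review named, but its use in the analysis is not.
- Analysis (14.3): no drug covariate, no on-drug or off-drug condition for success, and no rule for patients who change drug or are re-ablated.

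**2. Effect on the success rate (assumed inputs)**

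Let s be true ablation success, q the share of failures given a drug change, and r the share of those who respond and are then counted as successes.

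Apparent success = s + (1 − s) × q × r, with q from 0.5 to 1.0 and r from 0.2 to 0.5:

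- s = 0.8: 0.8 + 0.2 × 0.5 × 0.2 = 0.82, up to 0.8 + 0.2 × 1.0 × 0.5 = 0.90
- s = 0.7: 0.73 to 0.85
- s = 0.5: 0.55 to 0.75

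The excess is 0.02 to 0.25. Multiplied by 15, that is 0.3 to 3.75 patients.

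**3. Effect on burden in one patient (assumed inputs)**

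Take a burden of 20% and a drug that lowers it by 30% to 50%. If the drug is added between the recordings and the ablation did nothing, the 3-month burden is 20% × 0.7 = 14% to 20% × 0.5 = 10%. That is an apparent fall of 6 to 10 points. One such patient is 1/15 = 6.7% of the cohort. The arithmetic reverses if a drug is withdrawn.

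**4. How few patients decide the planned test**

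If all b discordant pairs favour improvement, the exact two-sided McNemar p is 2 × 0.5^b. For b = 5 this is 0.0625, and for b = 6 it is 0.031. Six patients therefore cross the 0.05 threshold in 14.3. Suppose the ablation had no effect and a drug change improved each patient independently with probability 0.10, 0.20, 0.25 or 0.50. The chance of six or more improving among 15 is then 0.002, 0.06, 0.15 or 0.85.

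**5. Why analysing only patients with unchanged drugs does not work**

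Assume 70% true success, that successes keep their drugs, and that a share c of failures have a drug change. Success in the unchanged group is 0.70 / [0.70 + 0.30 × (1 − c)].

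- c = 0.5: 0.70 / 0.85 = 82%
- c = 1: 0.70 / 0.70 = 100%

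The restriction would overstate success by 12 to 30 points.

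**The case against.** Several points on the other side have weight.

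- **No burden comparison is written down.** Section 14.3 does not describe a Holter-to-Holter analysis. McNemar's test is for binary data, and 10.3 describes the ward recording as a source of arrhythmia templates and their frequency for localisation. This stands: the comparison is an inference. It is a reasonable one, since reduction needs a starting value and the Holter is scheduled both before and after. That the baseline, metric and threshold are undefined is a gap in its own right.
- **Early recurrence may already count as failure.** Section 14.3 groups patients by symptoms and documentation during follow-up, so a documented recurrence before a drug change might put the patient in the recurrence group. That would protect the success rate, though not the burden change. The text does not settle it: mild recurrence can still be success, and 10.5 assesses recurrence by the Holter under its 3-month heading.
- **Drug data may exist anyway.** A reader might infer that baseline drug state is never captured. The documents do not support that. The past-history item could include drugs, hospital notes may hold them, and the CRF is not among the documents. What stands is that medication is not a specified baseline item, and history-taking does not require dose or last-dose time at the recording.
- **Drug use at entry is not shown.** A reader might take uptitration in 6.2 as proof that some patients enter on anti-arrhythmic drugs. It suggests this, but the sentence lists options for treating recurrence and does not describe the population.
- **Limited materiality.** This is a secondary endpoint in an unpowered pilot that section 14 calls descriptive. That lowers the priority, but 6.2 still makes the causal reading and 14.3 still sets a significance threshold.

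**Conclusion.** The concern holds in a limited form. Followed as written, the plan can count a drug effect as an ablation effect in the 3-month clinical outcome, because drug changes are allowed, drug state is not a named item before ablation, and the success rule does not refer to it. The size cannot be derived from the documents. The 2 to 25 point range rests on assumed success, drug-change and drug-response rates, and on drug-controlled recurrences being counted as successes. The direction may differ between patients. A recording provoked under 10.3 would add a further difference between baseline and 3 months.

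The documents do not support saying that the outcome is irretrievably confounded, or that only patients in the same drug state can support a claim about ablation. The primary safety and procedure-time endpoints are untouched. The point should be fixed before recruitment, when it costs little.

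**What to change.** **Data (10.2, 10.3 and CRF).** At the pre-ablation Mortara recording, record anti-arrhythmic and rate-slowing drugs, dose and time of last dose, and whether the recording was provoked and by what. Record the same drug fields at the 3-month Holter. Between the two, record the date of and reason for every drug change or re-ablation.

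**Analysis (14.3).**

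- Report the 3-month outcome and the burden change for all 15 patients.
- Split success into that reached without, and that reached with, a new or increased anti-arrhythmic drug or re-ablation. Do not count the latter as success of the index ablation.
- List patients whose drugs were reduced or stopped, with the direction of change.
- Do not limit the ablation claim to patients whose drugs were unchanged.
- State the baseline recording and the burden measure used. Reconcile the 6-month visit named for McNemar's test with the 3-month schedule.

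**Cost.** A few CRF fields, a short addition to 14.3, and possibly a lower reported success rate. No change to how drugs are given or withheld is proposed.

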11.2 Radiology or any other procedure(s)

All patients will undergo a cardiac CMR or CT exam to be used as a roadmap during the ablation procedure. The CT exam will comprise of a standard-of-care contrast-enhanced scan to visualise the cardiac chambers. This pre-procedure imaging is necessary in order to define the spatial anatomical relationship of the cardiac chambers. In the event that the ablation procedure needs to be repeated during follow-up, the roadmap scans can be re-used.

As part of a conventional PVC/VT ablation procedure, the patient is exposed typically to about 2 mSv of ionizing radiation, occasionally increasing to 10 mSv or more, per procedure. If radiation is necessary to be used during any of the study procedures than efforts will be made to lower the exposure to as low as reasonably achievable including the re-use of the CT or CMR scan for 3D image integration during the ablation procedure(s).

- ***Techniques and Interventions***

The technique of mapping the ventricular chambers/epicardial space in order to guide the PVC/VT ablation is a conventional procedure which is carried out routinely in the catheter labs using different mapping system according to operators' experience and confidence. The here proposed study will use the Vivo™ (Catheter Precision, Inc., USA) in the pre-invasive phase in order to guide ablation.

- ***Tools***

All tools used for the ablation procedure will include standard materials for ablation of PVC/VT. The Vivo™ Anatomy and Analysis software and the Kinect Camera are fully CE marked.

- ***Study Drugs***

This section does not apply.

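### The 3-month clinical outcome is read as the effect of the ablation, but section 14.3 has no rule for patients whose recurrence was treated before that visit

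*Combined protocol and SAP*

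**What the plan says.** **Treatment of recurrence.** Section 6.2 states: "Early recurrences will be treated by uptitrating/changing/addition of anti-arrhythmic medication and/or DCCV if persistent arrhythmia". The next step is: "If further arrhythmia occurs despite these measures, a re-ablation procedure will be offered". No date is attached to either step. Section 11.2 shows that a second procedure may fall inside follow-up: "In the event that the ablation procedure needs to be repeated during follow-up, the roadmap scans can be re-used".

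**Endpoint.** Section 14.2.2 lists, as a secondary endpoint, "To assess clinical outcome (suppression of reduction of PVCs burden/VT at 3 months F/U". The chart in section 10.5 says of the 3-month visit: "Assess recurrences by 12-lead Mortara Holter". Section 6.2 justifies the 3-month period as long enough to show what the ablation has done to arrhythmia burden, so the result is attributed to the ablation.

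**Analysis.** Section 14.3 uses the clinical outcome in three main ways:
- a percentage of patients "free from symptomatic or documented arrhythmia or with only mild symptoms related to arrhythmia recurrence";
- a split into success and recurrence groups, based on symptom severity and on tachycardia documented during follow-up, with no cut-off;
- a Cox model for freedom from PVC/VT, with no stated event definition, time origin or censoring rule.

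None of the three mentions added drugs, DCCV or repeat ablation. Section 14.6 adds no further statistical considerations.

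**The concern.** A 3-month Holter in a patient who has since had a new drug, a cardioversion or a second ablation shows the combined effect of the index procedure and the later treatment. If that patient is counted as a success, the index VIVO-guided ablation is credited with an effect that it did not produce alone. The error can only run toward success.

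The same classification feeds the comparison of baseline and procedural variables between success and recurrence groups, the analysis linking acute success to outcome, and the comparison of outcome with matched earlier procedures. Section 14.1 says that the pilot is meant to lead to an adequately powered multicentre trial, so an inflated rate could carry into its planning. With no rule fixed in advance, two analysts could also derive different success rates from the same data.

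**Working it through.** The plan gives no recurrence rate, rescue rate or success threshold, so it has no figure to reproduce. The check has two parts.

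**1. Where a rescued patient lands under section 14.3**

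| Patient before the 3-month visit | Success percentage | Success/recurrence split | Cox model |
|---|---|---|---|
| Documented VT, cardioverted, quiet at 3 months | Unclear: arrhythmia was documented, but no period is stated | Probably recurrence | Probably an event |
| Recurrent PVCs, drug added, low burden at 3 months | Can be success | Unclear: tachycardia does not plainly include PVCs | Unclear: event undefined |
| Symptomatic recurrence, drug increased, mild symptoms at 3 months | Can be success, through "or with only mild symptoms related to arrhythmia recurrence" | Unclear: no severity cut-off, and no statement whether the worst or latest severity counts | Unclear |
| Repeat ablation during follow-up, quiet at 3 months | Unclear: no single-procedure condition | Depends on what was documented | Unclear: no rule for a second procedure |

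Rows two and three are the clear gap. The time of judgement is itself unsettled: section 14.3 refers to a 6-month visit for within-patient improvement, while sections 6.1 and 10.4 end follow-up at 3 months.

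**2. Size**

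Input from the documents: n = 15 (section 14.1). Each patient carries 1/15 = 6.7 percentage points.

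Exact (Clopper-Pearson) 95% intervals at n = 15:
- 14/15 = 93.3% (68.1 to 99.8)
- 12/15 = 80.0% (51.9 to 95.7)

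Reclassifying two patients therefore moves the estimate by 2 × 6.7 = 13.3 points.

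For a range, let r be the proportion with an early recurrence that is treated, and s the share of those controlled at 3 months. Both are assumptions.
- Rescue counted as recurrence: success = 1 − r
- Rescue ignored: success = 1 − r + r·s
- Difference: r·s

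| r | s | Rescue = recurrence | Rescue ignored | Difference |
|---|---|---|---|---|
| 10% | 50% | 90% | 95% | 5 points |
| 20% | 70% | 80% | 94% | 14 points |
| 40% | 90% | 60% | 96% | 36 points |

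In the middle row, the expected number affected is 15 × 0.14 = 2.1, and the chance that at least one patient is affected is 1 − 0.86^15 = 0.90.

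These differences are upper values for each r and s, because they suppose that section 14.3 catches none of the rescued patients. If it catches a share c, the difference becomes r·s·(1 − c). The documents give no basis for c. With c = 50%, for example, the range of 5 to 36 points becomes 2.5 to 18.

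**The case against.** The strongest reply is that the plan is silent, not wrong. A reader might infer that it counts 3-month burden whatever was given in between, or that it declares rescued patients successes. No section says either. Section 14.3 in fact points partly the other way. Tachycardia documented at any time in follow-up bears on the success/recurrence split, and a time-to-event analysis would naturally count an early recurrence when it occurs. A patient cardioverted for persistent arrhythmia would very likely be caught. This stands, and it confines the clear gap to PVC recurrences and to recurrences made mild by drugs. It does not close that gap, because neither device defines the event and the percentage tolerates mild symptomatic recurrence.

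The chart entry "Review therapy, allow Re-ablation if necessary using same methodology" might be read as showing re-ablation before the endpoint. It does not: it belongs to the 3-month visit, and section 10.4 likewise ties a change of therapy or repeat ablation to a high burden found then. That repeat ablation can come earlier rests on section 11.2, together with the undated sequence in section 6.2.

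A reader might also infer that three rescued patients would turn 12/15 into 15/15. That requires every rescue to succeed, no other patient to fail, and none of the three to be classed as recurrence. It is a best case built on stacked assumptions.

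The stakes are limited too. This is a secondary endpoint in an unpowered pilot that section 14 calls descriptive, and section 6.1 gives the historical cohort no follow-up. The primary procedure-time and safety endpoints are untouched.

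Finally, counting rescue as failure is not the only legitimate choice. Observed status regardless of rescue, with rescue tabulated, is another, but it describes the whole treatment course and not the index ablation. Either way, the choice has to be stated in advance.

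**Conclusion.** The concern holds in limited form. Treatment of early recurrence before the 3-month assessment is planned, the result is attributed to the ablation, and no rule prevents a rescued and controlled patient from counting as a success of the index procedure. The route is clearest for recurrent PVCs and for recurrences made mild by added drugs; documented VT recurrences would probably be captured.

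Each affected patient raises the reported rate by 6.7 points. The illustration of 93% against 80% rests on an assumed two patients. The range of 5 to 36 points rests on assumed r of 10 to 40% and s of 50 to 90%, with nobody caught by the existing wording. This merits correction before analysis because the bias runs one way and the remedy is cheap, but it does not touch the primary endpoints.

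**What to change.** In section 14.3:

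1. Define success as success of the index procedure without rescue. A patient who receives a new or increased anti-arrhythmic drug, DCCV or repeat ablation for recurrent arrhythmia before the 3-month assessment counts as a recurrence in the success percentage, the success/recurrence split and the Cox model.
2. Date the event at first documentation of the recurrence, or at the start of rescue if no earlier date is documented. Dating every event from treatment would delay event times, since recurrence comes first.
3. State that this rule takes precedence over the wording that accepts mild symptoms. Otherwise the two conflict for a patient whose drug is changed for a mild recurrence.
4. Report observed 3-month burden as a supportive result, split by whether rescue was given, with counts by type of rescue.
5. Record the date and reason of interim drug changes on the CRF. Section 10.4 provides only for a medication review at 3 months, and no section asks for these details. Inpatient admissions, including elective ones, already fall under the SAE definition in section 12.1, so most repeat procedures should be traceable.

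The cost is a few sentences in the SAP, one added CRF field and a lower reported success rate. The change concerns classification and reporting only; patient care is unchanged. It does not supply the missing success threshold or resolve the reference to a 6-month visit, which need their own correction.
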